4.2 Selection of study population

4.2.1. Newly diagnosed HIV-positive individuals over the age of 18 and not pregnant, receiving HIV care from one of the health facilities participating in the trial

4.3 Randomisation and blinding

4.3.1. Patients were randomised through the REDCap system with no blinding

5. SAMPLE SIZE

Recruitment for this trial showed that achieving a sample size for any sub-group analysis is difficult to achieve with an app limited to a subset of smartphones in circulation and several other eligibility criteria on age, residence, literacy, and having a smartphone with data. Section 7.1. shows the flowchart of the HIV cases as they are screened and assessed for eligibility, then randomised and followed up. Priority groups of interest to this trial are males and young HIV clients aged 18-30 years, and it is exactly these two groups which are also more difficult to screen for eligibility as they use HCT services to a lesser extent.

The recruitment over approximately 8 months is expected to be able to recruit about 350 individuals. While it would be desirable to recruit a larger sample, as decision was made to stop at a time when sufficient sample is achieved to detect any effectiveness of the app (based on a 20% difference in linkage to care between the intervention and control arm, an 80% power with significance level of 0.05). At this sample size, it will be possible to see any trends in linkage to care in the priority sub-groups (males, youth) between the two trial arms, but the sub-groups will not be large enough to detect a 20% difference with statistical accuracy.

6. GENERAL ISSUES FOR ANALYSIS

STATISTICAL ANALYSIS PLAN

SmartLtC: Does an Android Smartphone App Increase Linkage To Care in Johannesburg

6.1 Software to be used for analysis

STATA

We will use Stata software (version 13.1, STATA Corp, College Station, Tex.) for statistical analysis.

6.2 Multicenter study data

This trial is individually randomised but since it is multi-centre it has a clustering aspect which needs to be taken into account in the analysis of outcomes. This clustering is linked to patient population/catchment specificities at the sites as well as facility related characteristics which may differ across the sites. Clustering could theoretically occur within the intervention arm across sites (app training done differently, different information provided the respective field worker despite scripted patient-fieldworker interaction, etc.). However, we believe that the more relevant clustering occurs in both the intervention and control arms, and is an effect of the different sites' patient and service characteristics. We therefore envisage to use a random effects model (sometimes referred to as "random intercept" model - Lee, K and Thompson, S. The use of random effects models to allow for clustering in individually randomised trials. *Clinical Trials* 2005; 2: 163 – 173). This is a realistic model for any clustering across both treatment arms in which it is probable that the clustering is unlikely to have an impact of the treatment effect.

6.3 Exposure variable/s:

6.3.1. A smartphone health application (SmartLink), created by the study team, which provides patients with their CD4 count and viral load, along with explanatory descriptions and HIV/AIDS information.

6.4 Derived and computed variables

6.4.1. Derived variable:

- Age - Based on date of birth

6.4.2. Computed variable:

- Length of time between first and second NHLS blood test

6.5 Data transformations

6.5.1. Not expected if sample is normally distributed

6.6 Statistical tests to be conducted

6.6.1. Descriptive analyses

6.6.1.1. Comparison of means

6.6.2. Inference statistical analyses

6.6.2.1. Pearson's exact

6.6.3. Modeling (random effects to allow for multisite design)

6.7 Methods for dealing with withdrawals, missing data, outliers

6.7.1. Withdrawals/opt-outs will be considered loss-to-follow-up

STATISTICAL ANALYSIS PLAN

SmartLtC: Does an Android Smartphone App Increase Linkage To Care in Johannesburg

[figure not shown]
- 6.7.2. As REDCap is used as the data collection tool, minimal missing data is expected. If missing data is found, the study team will contact the study participant by telephone.
- 6.7.3. Outliers will be identified using STATA and either removed or replaced with average values on a case-by-case basis.

STATISTICAL ANALYSIS PLAN

SmartLtC: Does an Android Smartphone App Increase Linkage To Care in Johannesburg

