The aim of the study is to show that smartphone apps work for that proportion of the population that currently have Android smartphones, not that it works for the general population. Smartphone purchase is rapidly increasing in South Africa, with 75% of new cell phones sold in South Africa currently being smart phones. We expect that randomization and a large sample size will enable us to have a reasonable balance between the arms, unless participants randomized to the control group request study withdrawal due to not getting the app.

Sample Size

Based on a primary endpoint of a second HIV-linked laboratory test (CD4, viral load) being performed at a clinical facility, within 8 months after the HIV-positive result, suggesting successful attendance and entry into HIV care, we anticipate at least 1000 patients in each arm will be needed. The study team expects to see a 20% difference in linkage to care levels through the app (using a second HIV-linked laboratory test as an indicator for linkage to care). The sample size is calculated based on 80% power, 0.05 significance with a loss-to-follow-up rate of approximately 27% (Hillbrow CHC data). Both ART and pre-ART patients will be expected to return for a follow-up laboratory test around 6 months after diagnosis; ART patients for a viral load, and pre-ART for a follow-up CD4 count.

In South Africa, both younger and male clients have lower linkage to care rates than females and individuals over 25. In order to conduct subgroup analysis on these higher-risk populations (young people and men), there will be an over-sampling of male patients and those between the ages of 18 (the age of majority) and 25 for both the intervention and control arms given that it has been shown that these groups are less likely to access health services efficiently (Kranzer, 2010). These populations will be recruited until 250 of these individuals are included in both arms to ensure the study is powered to analyse the effect in these key subgroups. Based on a 20% difference in linkage to care for the intervention/app arm with an 80% power, a significance level of 0.05 and a loss-to-follow-up rate of 40% a sample size of 97 per arm is required. Again, the study team will over-sample based on the proof-of-concept nature of the study.

Figure 2: *Recruitment flow chart*

App specifications

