³ For example, if a CD4 count of 250 is returned, the number will be shown in red with an informative note explaining that that CD4 value is abnormally low and request that the patient attend to the clinic for further care as soon as possible. Alternatively, if the a CD4 count result of 700 is returned, the number will be shown in amber (a warning colour) with an informative note explaining that the CD4 count value is within the normal range and they should return to the clinic for wellness counselling and then have another CD4 count test in 6 months. For any result (CD4 or viral load) the patient will be able to get more information about HIV/AIDS, CD4 counts and viral loads within the app, see a list of frequently asked questions (FAQ), given clickable links to get external (web) information or provided contact numbers for the study team (for study or app-related questions) or the National HIV/AIDS helpline (for HIV-related questions).

Baseline recruitment will include questions on basic demographics. Throughout the study the team will monitor the number of times the app is accessed to view laboratory results and/or support information by the user; and loss-to- follow-up. Healthcare monitoring, measured by appropriate laboratory adherence to treatment guidelines, will be monitored through the NHLS database; in particular, we will monitor whether providing information to the patient to prompt the health care worker improves compliance with guidelines. All patients who exit from the trial will be given a survey that includes questions to assess CD4 count and HIV knowledge, health status, health care access, and patient satisfaction with the app, as well as with the health care services. This will allow us to compare how much the app has contributed to linkage to and retention in care, as well as to patient understanding of their health management.

After 8 months of participating in the study the research team will monitor participant attendance to a follow-up laboratory test through the NHLS test database. The patient will not be contacted at this point. Data will be analysed comparing the standard of care arm with the intervention arm.

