- Total annual per patient cost of providing a comprehensive model of ART linkage to care using the smartphone app (receiving laboratory results and linkage-to-care) plus cost over 10 years

Cost-effectiveness analysis involves the comparison of two or more competing methods in terms of both their costs and consequences. The outcome measure of the cost-effectiveness work will be the cost of ART initiation with a particular intervention in South African Rand (ZAR) per disability adjusted life year (DALY) averted. The lower the cost per DALY averted, the more cost-effective the intervention. It will be based on a 5% discount rate.

For each target and cost scenario, this analysis will be able to provide the estimated impact in terms of OI and AE averted, impact in HIV stage defined by CD4 count and treatment costs and deaths averted due to ART linkage to care of those using the smartphone app.

Participant opt-out

All participants will be provided with contact information for the study team and will be informed that they can drop out of the study at any time with no consequences (as per Good Clinical Practice guidelines). Should a participant request to withdraw from the study the team will identify their informed consent sheet and mark it accordingly, remove the patient's data from REDCap and notify the NHLS if they are part of the intervention arm to ensure they will not receive additional notifications of laboratory results. The participant will be asked if they would like to keep their username and password active to access the app in the future; their account will be deleted or kept accordingly.

Safety considerations

Accidental disclosure (through phone loss/theft/borrowing or any other method) will be limited by the study team as much as possible. This will be done actively by having a username, password AND PIN code for app use. Additionally, the recruitment team will inform participants of the sensitive information on the app and request that they don't share it with

anyone. Lastly, the app icon and name will not relate to health or HIV in any way; only after the username and password is entered will health-related terminology be used.

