The primary outcome, linkage to care around 6 months after initial diagnosis, will be available after the final patient recruited has reached the 8 month mark, allowing immediate assessment of the feasibility and immediate impact of the app on initial linkage to care. Thereafter, retention in care, defined as continuation of HIV care (regular clinic visits with laboratory tests and/or medicine pickup) after the linkage to care visit will be assessed 12 months after linkage to care had been made.

Analysis will be done by the study team using STATA. Intention-to-treat will be the primary approach of the analysis and all missing data points will be considered to be loss-to-follow-up. Analysis of the primary outcome will be based on a chi-squared test comparing the proportion of individuals between the study arms and within study sites. A

logistic regression model, with linkage to care as the dependent variable, will be a secondary analysis of the primary outcome.

For secondary outcomes, chi-squared tests will be used for binary variables, Mann-Whitney-U tests for non-normally distributed variables, and t-tests for continuous variables. Relative risk calculations (at 95% confidence) will be used to compute binary variables. Survival analysis will be conducted to determine linkage outcomes at 6 months. A sensitivity analysis will be conducted using regression analysis to identify and adjust for potential confounders.

For the cost-effectiveness analysis, we will have data on direct costs and understand the resource requirements for the development of the app. We will corroborate our existing estimates of the smartphone data costs of the patient. The study team will collect data on clients' opportunity cost as part of the end of the study participant interview as linkage to care (as opposed to non-linkage to care) actually takes more time. We will use primary data collect through this study to calculate unit costs associated to providing HIV services.

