3.4 Primary outcome variable/s

3.4.1. Attendance to a second NHLS blood test within 8 months

3.5 Secondary outcome variable/s

3.5.1. Attendance to a second NHLS blood test

3.5.2. Length of time between first and second NHLS blood test

3.5.3. Attendance to a second NHLS blood test within 8 months

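### SAP 6.7.1 and the protocol's opt-out procedure treat withdrawals in ways that cannot both operate; if opt-outs count as not linked and are commoner in control, the rule favours the app

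*SAP*

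**What the plan says.** The SAP's rule for withdrawals (6.7.1) is one sentence: "Withdrawals/opt-outs will be considered loss-to-follow-up". It does not say how a lost participant enters the numerator or denominator of the primary outcome, which is yes/no: "Attendance to a second NHLS blood test within 8 months" (SAP 3.4.1).

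The protocol's Analysis plan states: "Intention-to-treat will be the primary approach of the analysis and all missing data points will be considered to be loss-to-follow-up".

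The protocol's Participant opt-out section says that when someone asks to withdraw, the team will "remove the patient's data from REDCap and notify the NHLS if they are part of the intervention arm".

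Just before its Sample Size section, the protocol expects reasonable balance between arms, "unless participants randomized to the control group request study withdrawal due to not getting the app". It gives no rate. SAP 4.3.1 confirms that there is no masking: "Patients were randomised through the REDCap system with no blinding".

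Under Patient follow-up, the protocol says that at 8 months "the research team will monitor participant attendance to a follow-up laboratory test through the NHLS test database", and that the participant is not contacted at that point.

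**The concern.** Leaving the study is not the same as leaving HIV care. A person who opts out may still have a second test on the NHLS record. If that person is counted as not linked, the rule overrides an outcome that may be known. If it happens more often in control, it lowers the control rate more than the app rate and produces a difference that the app did not cause.

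The only withdrawal mechanism that the documents name is specific to control, and participants know which arm they are in. The plan has no sensitivity analysis for withdrawals and no report of opt-outs by arm, so a reader of the results could not tell how much of a difference came from scoring. Because the two documents point to different handling, the choice could also be made after the unblinded data are seen.

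**Working it through.** **Step 1. The passages side by side.**

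- SAP 6.7.1 with the protocol's Analysis plan: opt-outs are lost to follow-up and analysis is by intention-to-treat. SAP table 7.4 has one n and % row for attendance and no row for lost participants. If everyone randomised stays in the denominator, a lost participant can only count as not attended. This is an inference, but the natural one.
- Protocol, Participant opt-out: the data are removed from REDCap. A removed participant is in neither numerator nor denominator.
- A participant cannot be both removed and counted as lost.

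**Step 2. Inputs.** The documents give no opt-out figure to reproduce, so ranges are used.

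- Arm size: SAP section 5 expects about 350 in total. 175 per arm assumes 1:1 allocation, which is not stated.
- Linkage p: 50-55% (Protocol, Population); midpoint 52.5%.
- Opt-out share w: assumed, control only in the base case.
- Share of opt-outs who would in fact link, q: assumed equal to p in the base case (opt-out unrelated to linkage).
- True app effect: none. Test: two-sided chi-squared at 0.05.

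**Step 3. Opt-outs counted as not linked.** The spurious difference is w_control × q_control − w_app × q_app. With 5% control-only opt-out: 0.05 × 52.5 = 2.6 points, so control reads 52.5 − 2.6 = 49.9%. With 10%: 0.10 × 52.5 = 5.25, shown as 5.3 points, so control reads about 47.3%. Rejection rates come from exact enumeration of both binomial counts.

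| Control opt-out | Participants (of 175) | Spurious difference | Rejection, two-sided | Favouring the app |
|---|---|---|---|---|
| 0% | 0 | 0 | 4.8% | 2.4% |
| 3% | about 5 | 1.6 points | 5.7% | 4.6% |
| 5% | about 9 | 2.6 points | 7.5% | 6.8% |
| 10% | about 18 | 5.3 points | 16.1% | 15.9% |

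Over 50-55% linkage, two-sided rejection is 7.2-7.7% at 5% opt-out and 15.0-17.2% at 10%.

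**Step 4. Relaxing the assumptions.**

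- Opt-out in both arms, 10% control and 5% app, q = p: (0.10 − 0.05) × 52.5 = 2.6 points.
- Equal opt-out with the same q in both arms: 0.
- Opt-outs who would never link (q = 0): 0.
- 10% control-only opt-out, linking at half the average rate (q = 26.25%): 0.10 × 26.25 = 2.6 points, with 6.8% favouring the app.

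**Step 5. Opt-outs excluded.** The observed control rate is (p − w × q) / (1 − w). With w = 10%:

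- q = 52.5%: 0.4725 / 0.90 = 52.5%; no bias.
- q = 26.25%: (0.525 − 0.02625) / 0.90 = 55.4%; 2.9 points against the app.
- q = 80%: (0.525 − 0.08) / 0.90 = 49.4%; 3.1 points towards the app.

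Exclusion is therefore unbiased only if opting out is unrelated to linkage.

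**Step 6. NHLS outcome used.** If opt-outs are scored from NHLS, the expected difference is 0 whatever w and q are. In simulation at 5%, 10% and 20% control-only opt-out, the chance of a significant result favouring the app was about 2.4%.

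**The case against.** A reader might infer that the SAP scores opt-outs as failures. It does not say so. It uses an undefined term, and the protocol also uses loss to follow-up as a sample-size allowance (27% and 40%), which, like removal from REDCap, points to exclusion. Under exclusion with opt-out unrelated to linkage, the bias is zero. This stands as a limit on the claim. It does not settle the plan, because the two texts still conflict and exclusion has its own condition (step 5).

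A reader might also infer that the protocol expects disappointed controls to leave. It expects balance and names their withdrawal as an exception, without a rate. App users could opt out too: they receive notifications and carry the disclosure risk that the protocol discusses under Safety considerations. Control-only opt-out is an assumption, and the table shows its unfavourable end.

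Third, 6.7.1 concerns people who withdraw from the study, not those who merely stop opening the app. The protocol's Recruitment section makes laboratory monitoring a condition of taking part, so withdrawal may end that permission. This stands. Use of NHLS results after withdrawal depends on consent, and the consent form was not available here.

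**Conclusion.** The plan does not settle how withdrawals enter the primary outcome, and its two statements conflict. On the most natural reading of the SAP, an excess of control opt-outs would favour the app. With 175 per arm, 52.5% linkage, no app effect, and control-only opt-out unrelated to linkage, the spurious difference is 2.6 points (7.5% rejection) at 5% opt-out and 5.3 points (16.1%) at 10%. It is zero if opt-out is equal across arms with similar linkage, or if those who opt out would never link.

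The documents do not support a conclusion that the primary result will be biased towards the app. That would need a known scoring rule and a known excess of control opt-outs who would have linked, and they give neither. Confidence is medium. The change should be made because it protects the result whatever the opt-out rate turns out to be.

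**What to change.** Reconcile SAP 6.7.1 with the protocol's Participant opt-out section, before the arms are compared:

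1. Keep the randomised record (arm, site, sex, age) of those who withdraw, where consent allows, instead of removing it from REDCap.
2. At opt-out, ask whether NHLS results may still be used. Score those who agree from NHLS, like everyone else.
3. Treat as missing only those who withdraw laboratory permission, and report their number by arm. Name one primary handling for them in the SAP; imputation within arm from site, sex and age is a workable choice.
4. Add sensitivity analyses that (a) exclude them, (b) score all as not linked, and (c) score control withdrawals as linked and app withdrawals as not linked.
5. State in the report whether the primary conclusion depends on how control opt-outs are scored.

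The cost is a rewritten SAP paragraph, a small change to the opt-out procedure with one added question, and a short sensitivity table. A few outcomes will stay missing, including those of anyone who withdrew before the question was introduced; SAP 4.3.1 describes randomisation in the past tense, so there may be some. The estimated effect may be smaller than under the failure rule.

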7. TABLES, FIGURES AND LISTS

7.1 SAMPLE SIZE TABLE

7.2 DUMMY TABLES FOR PARTICIPANT DEMOGRAPHICS

Characteristic	Data
Age (years)	Mean, Standard Deviation, Median, Range
Gender	Percentages
Highest education received	Mean, SD, median, range

STATISTICAL ANALYSIS PLAN

SmartLtC: Does an Android Smartphone App Increase Linkage To Care in Johannesburg

LSM (Socio-economic scale)	Mean, SD, median, range
Employment status	Frequency, percent in each status

7.3 Tests for homogeneity

Characteristic	Intervention arm	Control arm	Statistical significance (p value)
Mean age (SD)			
Mean education received			
Mean LSM (SD)			
Employment status (n, %)			

7.4 Testing H₀ of main and secondary hypothesis'

Characteristic	Intervention arm	Control arm	Statistical significance (p value)
Attendance to second blood test within 8 months (n, %)			
Attendance to second blood test (n, %)			
Length of time between first and second blood test (SD)

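### SAP Table 7.4 tests the interval to the second blood test among attenders only, so that row conditions on the outcome the app is meant to change

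*SAP*

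**What the plan says.** SAP 3.5.2 lists "Length of time between first and second NHLS blood test" as a secondary outcome, and SAP 6.4.2 names the same quantity as the one computed variable. Neither gives a time limit or a value for a participant with no second test. The 8-month limit is attached only to the attendance outcome. The hypothesis-testing table in SAP 7.4 then has the row "Length of time between first and second blood test (SD"), with a column per arm and a p value column.

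SAP 6.6 lists a comparison of means (under descriptive analyses), a Pearson's exact test (under inference) and "Modeling (random effects to allow for multisite design"). None of these is a time-to-event method.

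The protocol's Analysis plan makes intention-to-treat the primary approach. For secondary outcomes it names "Mann-Whitney-U tests for non-normally distributed variables, and t-tests for continuous variables". It also says: "Survival analysis will be conducted to determine linkage outcomes at 6 months". The SAP does not carry that survival analysis forward or link it to this row.

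**The concern.** An interval between two tests needs two tests. Whether a second test happens is decided after randomisation, and raising that chance is the purpose of the app. If the app works, the app arm's attenders include people who would not have come back without it, and the control arm's attenders have no counterpart to them. A difference in mean interval then mixes any real change in timing with a change in who is counted.

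At stake is one of the three results rows in Table 7.4. For the same true gain in linkage, its p value could make the app look slower, no different or faster. The attendance rows above it would show the unequal denominators, but not how far or in which direction the mean has moved.

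The missing time limit is a separate fault. The protocol's Patient follow-up section analyses linkage 8 months after the last recruit, and SAP 5 expects about 8 months of recruitment. Participants could therefore be observed for about 8 to 16 months, and which late tests enter the row depends on the data cut. The row also does not match the 8-month primary.

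**Working it through.** The plan gives no SD, effect size or power for this outcome, so there is no stated figure to reproduce.

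**Inputs from the documents**
- About 350 participants (SAP 5). The allocation ratio is not stated; 1:1 is assumed, giving 175 per arm.
- Control linkage 50-55% (Protocol, Population); midpoint 52.5%.
- Target difference 20% (SAP 5), read as percentage points, giving 72.5%.

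**Participants with no value**
- Control: 175 × (1 − 0.525) = 83.1, about 83.
- App: 175 × (1 − 0.725) = 48.1, about 48.
- Together about 131 of 350, or 37%, unequally split.

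**Shift in the attender mean.** Suppose the app does not move the date of anyone who would have tested anyway, and only adds attenders. Let *add* be the gain, *m* the mean day of the extra tests and *m0* the control mean. Then

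shift = (m − m0) × add / (0.525 + add).

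Assumed timings: early tests near day 95 (the protocol's Intervention section says some patients need bloods at 3 months) and the rest near day 185 (return at around 6 months). The early share *e* of control tests is not documented, so it is taken as 0, 25 or 50%, giving m0 = 185 − 90e. Gains of 10 to 20 points are shown.

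*Extra attenders near day 190*
- e = 0: m0 = 185. 5 × 0.10/0.625 = +0.8 days; 5 × 0.20/0.725 = +1.4 days.
- e = 25%: m0 = 162.5. 27.5 × 0.10/0.625 = +4.4; 27.5 × 0.20/0.725 = +7.6.
- e = 50%: m0 = 140. 50 × 0.10/0.625 = +8.0; 50 × 0.20/0.725 = +13.8.

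*Extra attenders near day 95*
- e = 0: −90 × 0.10/0.625 = −14.4; −90 × 0.20/0.725 = −24.8.
- e = 25%: −67.5 × 0.10/0.625 = −10.8; −67.5 × 0.20/0.725 = −18.6.
- e = 50%: −45 × 0.10/0.625 = −7.2; −45 × 0.20/0.725 = −12.4.

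*Extra attenders timed like controls:* m = m0, so the shift is zero.

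**How often the late case gives a significantly slower app.** These are simulated trials with a Welch t-test at two-sided 0.05, so 2.5% is expected in each direction by chance. The SD around each timing is also undocumented and was varied.

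| Early share of control tests | SD 15 days | SD 30 days | SD 45 days |
|---|---|---|---|
| 0% | 6-10% | 4-5% | 3-4% |
| 25% | 12-29% | between the other rows | between the other rows |
| 50% | 22-57% | 19-47% | 14-35% |

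The protocol's Mann-Whitney option does not help: at SD 15 it gives 6-9%, 12-29% and 22-54% for the three rows. With extra attenders timed like controls, the rate was 2-3% in each direction.

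**The remedy under the same late scenario.** A site-stratified log-rank test was run on all randomised participants, censored at day 243. It assumed four sites with 60, 50, 35 and 30 per arm, control linkage of 45, 50, 58 and 65%, and SD 15. It favoured the app in 34-41%, 65-75% and 89-96% of trials at gains of 10, 15 and 20 points, and never significantly favoured control. The primary chi-squared test has about 47%, 82% and 97% power at the same gains.

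**The case against.** The strongest defence is that the protocol already plans intention-to-treat and a survival analysis of linkage, and that SAP silence does not cancel either. It adds that SAP 6.6 files the comparison of means under description, that the attendance rows show the denominators, and that the outcome is secondary. Much of this is fair, and it limits the weight of the point. But Table 7.4 still puts a p value on this row, and nothing in the SAP says the p value comes from an analysis that includes participants without a second test. The protocol's survival analysis also refers to 6 months, whereas the primary outcome uses 8.

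A second objection is that the larger error rates come from assumed timings. That also stands. The protocol expects both patient groups back at around 6 months. In the closest scenario, with no early tests and extra attenders near day 190, the shift is about 1 day and the excess of false results is small.

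Three stronger readings are tempting, and the documents do not support them.
- **That the missing time limit itself breaks the randomised comparison.** It does not, because randomisation balances length of observation between arms. Conditioning on attendance is the fault; the missing limit leaves the variable poorly defined.
- **That the row will make the app look slower.** No timing data are given, so the direction is open. If extra attenders come early, a finding of faster also agrees in direction with an analysis of everyone.
- **That tests after 8 months add a bias that can be sized.** The documents give no rate of late testing, and the 12-month participant follow-up depends on funding. If the app only brought late testers forward, with equal numbers of attenders per arm, the shorter mean would be a true speed-up.

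**Conclusion.** The point holds. As written, the time row of Table 7.4 tests a quantity defined only after the outcome the app targets has occurred, so its p value is not a randomised comparison. That conclusion needs no timing assumption.

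The size does. With 175 per arm and 52.5% v 72.5% linked, about 83 and 48 participants have no value. Across gains of 10-20 points and 0-50% early control tests, late extra attenders lengthen the app mean by about 1 to 14 days. The app is then called significantly slower in about 6-57% of trials at SD 15 days, 4-47% at SD 30 and 3-35% at SD 45. The low end applies when nearly all tests fall around 6 months, as the protocol expects. Early extra attenders shorten the app mean by about 7 to 25 days, and attenders timed like controls cause no bias.

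The primary endpoint is untouched. This should be corrected before analysis, but it does not threaten the trial's main result.

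**What to change.** - In SAP 3.5.2, 6.4.2, 6.6 and 7.4, define the outcome as time from first to second test in all randomised participants with available data, censored at 8 months.
- Carry over the protocol's survival analysis as Kaplan-Meier curves by arm, read at both 6 and 8 months. This reconciles the two horizons.
- Name one p value in advance that accounts for site. A site-stratified log-rank test is one choice. A survival model with a shared site frailty is another, and it keeps the random site effect of SAP 6.2 ("We therefore envisage to use a random effects model"). If the log-rank test is chosen, say that stratification replaces the random intercept for this row.
- Show the mean (SD) among attenders as a description, with n per arm and no p value.
- State that the test overlaps with the primary and describes timing, and that it has less power than the primary when gains come late.

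Withdrawals are a separate point that this analysis will meet. The SAP says "Withdrawals/opt-outs will be considered loss-to-follow-up", while the protocol's Participant opt-out section says the team will "remove the patient's data from REDCap". State the rule used and the number per arm without data. Where data have been removed, the analysis cannot be fully intention-to-treat.

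The cost is SAP wording and a little extra Stata code. NHLS results are already being collected and no participants are added. Tests after 8 months remain covered by the any-time attendance outcome in SAP 3.5.1.
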